#### **6.2 Treatment Exposure**

The number and percentage of participants administered each of the three (3) dose/volumes of gel at Visits 3, 5, and 7 will be displayed overall and by site. Participants will be classified into groups by dose/volume of gel based on the time from dosing up until just before the next higher dose/volume is administered (e.g., for the 4 mL dose/volume group, any safety endpoints which occur between the time of gel insertion at Visit 3 up until (but not including) the time the 16 mL dose/volume is administered at Visit 5.)

If applicable, the number and percentage of participants who had study product held during follow-up will be displayed overall and by site (along with the reasons why product was held).

#### 6.3 Protocol Deviations

Protocol deviations occurring in MTN-037 will be summarized in a table of each type of deviation by site and overall, and in a listing of deviation events.

These data will be reviewed prior to the analysis of the primary and secondary endpoints to determine if any protocol deviations in this study impact participant eligibility or treatment administration and subsequently necessitate adjustments to the analysis set.

# 7. BASELINE DATA

Baseline participant demographic characteristics such as age, sex at birth, ethnicity, race, height, weight, and body mass index (BMI) will be summarized and displayed in tables overall and by site, and in tables overall and by sex at birth. Descriptive statistics will be presented for age, height, weight, and BMI. Frequency counts and percentages will be presented for sex at birth, ethnicity, and race. No formal comparisons are planned.

Individual participant baseline characteristics (medical history and results from baseline anorectal exam findings, pelvic exam findings, STI results, hematology, and local laboratory results) will be presented in listings.

#### 8. SAFETY ANALYSES

All participants enrolled and administered a dose of PC-1005 will be assessed for safety.

#### 8.1 Primary Safety Analyses

The primary safety endpoint is defined as follows:

Grade 2 or higher AEs as defined by the Division of AIDS Table for Grading the Severity of Adult and Pediatric Adverse Events, Corrected Version 2.1, July 2017, and/or Addenda 1, 2 and 3 (Female Genital [Dated November 2007], Male Genital [Dated November 2007] and Rectal [Clarification Dated May 2012] Grading Tables for Use in Microbicide Studies).

The number and the percentage of participants experiencing each safety endpoint will be tabulated by dose/volume of gel. This table will display a summary for any primary safety endpoint and for each individual safety endpoint. Each participant will contribute once in each category (i.e., only for highest severity AE for each participant) for the calculation of event rates for each dose/volume of gel. Exact binomial confidence intervals (Clopper-Pearson) will be calculated for each safety endpoint, even if no events occur for an endpoint for a particular dose/volume.

#### 8.2 Adverse Events

Summaries of adverse events will include a cumulative listing of adverse events, a table displaying the total number of adverse events by severity grade and relationship to study product, a table of the incidence of adverse events by MedDRA organ system class/preferred term and severity, and a table of incidence of adverse events by MedDRA organ system class/preferred term and relationship to study product. Tables will be displayed by dose/volume, and listings will include the dose/volume period when the AE occurred.

#### 8.3 Laboratory Evaluations

The number and percentage of participants with a positive result for the following laboratory tests will be displayed in a table overall and by sex at birth: hCG for pregnancy and HIV. A listing of participants with positive results of STI testing (syphilis, trichomonas, gonorrhea, chlamydia) after dose insertion will be presented.

Hematology results after dosing with each dose/volume, including hemogram (hemoglobin, hematocrit, MCV, platelets, WBC) and differential (neutrophils, lymphocytes, monocytes, eosinophils, and basophils) results will be tabulated by dose/volume using descriptive statistics.

Serum chemistries (AST, ALT, and creatinine) after dosing with each dose/volume will be tabulated by dose/volume using descriptive statistics.

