4 STUDY DESIGN

4.1 Identification of Study Design

MTN-037 is a Phase 1, open label, sequential dose/volume escalation study

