10.7.2 Primary Analysis

When the use of descriptive statistics to assess group characteristics or differences is required, the following methods will be used: for categorical variables, the number and percent in each category; for continuous variables, the mean, median, standard deviation, quartiles and range (minimum, maximum). Within-treatment group assessment of the change from the baseline measurement to a follow-up measurement will be analyzed using McNemar's test (for categorical response variables) or the paired t-test or Wilcoxon signed-ranks test (for continuous variables).

Safety Endpoints

All visits in which a participant has been exposed to the study product will be included in the primary analyses of safety. Secondary intent to treat analyses may also be performed. The number and the percentages of participants experiencing each safety endpoint (see Section 10.2) will be tabulated by dose/volume of gel. Each participant will contribute once in each category (i.e., only for highest severity AE for each participant) for the calculation of event rates for each dose/volume of gel.

To assess the overall tolerability of the 3 dose/volumes of gel, participants in each dose/volume may be compared for characteristics including safety events and laboratory measurements using descriptive statistics. Due to the small sample size, formal comparisons will not be done.

Pharmacokinetic/Pharmacodynamic Analysis

We will use descriptive statistics such as the mean and median and corresponding 95% confidence intervals to describe the MIV-150 concentrations in all biological matrices assessed at all scheduled time points. For each dose/volume of gel, the 0.5 to 48 hour time points will be used to describe the concentrations beginning soon after a gel dose through time to peak concentrations through initial elimination among different matrices.

Concentrations will be compared among and between volume arms using paired analyses.

Ex vivo HIV explant data will use cumulative p24 to compare baseline with study product. Concentration-response relationships will also be explored using appropriate linear and non-linear models. Rectal lavage fluid will be assessed for anti-HIV activity and the percent inhibition will be correlated to MIV-150 concentrations.

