# 2.3.3 Sample Size and Power

The study is designed for a total accrual of twelve (12) participants, which gives sufficient power for the detection of events (adverse events or detection of drug) as described in the protocol. Descriptive safety analyses and pharmacokinetic analyses are planned with no formal statistical testing.

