# 5. GENERAL ANALYSIS METHODS

When the use of descriptive statistics to assess dose/volume group characteristics or differences is required, the following methods will be used: for categorical variables, the number and percent in each category; for continuous variables, the mean, median, standard deviation, quartiles, and range (minimum, maximum). Within-treatment group assessment of the change from the baseline measurement to a follow-up measurement will be analyzed using McNemar's test (for categorical response variables) or the paired t-test or Wilcoxon signed-ranks test (for continuous variables).

The following descriptions may be used to distinguish the dose/volume groups: "4 mL Volume", "16mL Volume", and "32 mL Volume".

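### SAP 8.3 tabulates laboratory safety results only after dosing and assigns no baseline comparison to them, so a within-person shift common to all volumes and below AE reporting appears in no table of SAP 7 or 8

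*SAP*

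**What the plan says.** **Laboratory tables.** SAP 8.3 covers blood counts with "Hematology results after dosing with each dose/volume, including hemogram" and chemistries with "Serum chemistries (AST, ALT, and creatinine) after dosing with each dose/volume will be tabulated by dose/volume using descriptive statistics". It names no baseline column, change from baseline or grade shift.

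**Baseline.** SAP 7 handles individual baseline findings this way: "hematology, and local laboratory results) will be presented in listings". No baseline laboratory table is specified.

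**General method.** SAP 5 states: "Within-treatment group assessment of the change from the baseline measurement to a follow-up measurement will be analyzed using McNemar's test", with a paired t-test or Wilcoxon signed-rank test for continuous variables. Protocol 10.7.2 carries the same sentence. Neither says which variables it applies to or which visit is the baseline.

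**Testing.** SAP 2.3.3 states: "Descriptive safety analyses and pharmacokinetic analyses are planned with no formal statistical testing".

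**Protocol on laboratory data.** Protocol 10.7.2 allows that "participants in each dose/volume may be compared for characteristics including safety events and laboratory measurements using descriptive statistics". That is an optional comparison between volumes and does not mention baseline.

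**Design.** Protocol 4.1: "MTN-037 is a Phase 1, open label, sequential dose/volume escalation study". SAP 2.3.3: "The study is designed for a total accrual of twelve (12) participants". Each participant is scheduled for 4, 16 and 32 mL in that order.

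**The concern.** With no placebo or untreated arm, the only internal reference for a laboratory value is the participant's own value before exposure. That value exists: CBC and AST/ALT/creatinine are required at Screening and again 24 hours after each dose (Protocol Appendix I). The laboratory output as specified does not bring the two together. Its columns can be compared only with each other, and the same people fill all three.

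The entry criteria sharpen this. Hemoglobin, platelets and AST/ALT must be below Grade 1 at Screening (Protocol 5.3), so a participant's values can rise or fall noticeably and still be ungraded, or reach only Grade 1 and so fall outside the Grade 2 or higher primary endpoint. At stake is whether this first rectal study of MIV-150 displays an early, mild, within-person laboratory signal.

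The clinical background gives modest support for looking. Protocol Table 8 reports jaundice among drug-related events at 1200 mg twice daily by mouth, and a clinically significant cholestatic hepatitis in the same study. The largest dose here is far smaller: from Protocol 6.3, 73.6 µg per 4 mL × 8 = 588.8 µg, or about 0.59 mg. Protocol 2.5 puts plasma levels after vaginal gel about 1,000-fold below those after oral dosing. Rectal exposure is not yet known.

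**Working it through.** **1. The plan's own figures.** The plan gives no figure for the laboratory analysis. Protocol Tables 18 and 19 describe event counts with n = 12. All Table 18 entries reproduce to one decimal, and the Table 19 limits agree within 0.1 point (for 0/12, the upper limit is 1 − 0.025^(1/12) = 26.46% against 26.4%). Neither is disputed.

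**2. What the planned columns can show.** Write a participant's result at volume v as y(v) = b + δ + e(v), and at baseline as y(0) = b + e(0). Here b is the person's own level, δ a shift common to all volumes, and e random variation.

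- Between volumes: E[y(16) − y(4)] = (b + δ) − (b + δ) = 0, and likewise for 32 against 4 mL.
- Against baseline: E[y(v) − y(0)] = δ.

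Simulation agrees. With n = 12, an assumed baseline-to-follow-up correlation of 0.7 and δ = 0.5 SD, the average 16 − 4 and 32 − 4 mL differences were 0.00 SD and the average 4 mL minus baseline difference was 0.50 SD.

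**3. The provisions side by side.**

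- SAP 8.3 followed as written gives post-dose summaries and no baseline contrast.
- SAP 5 applied to laboratory data gives a paired test, but the analyst must choose the baseline and depart from SAP 2.3.3.
- SAP 8.2 tabulates adverse events of all grades by volume. Protocol 8.3.1 allows an abnormal laboratory finding to be an adverse event and requires recording at any severity. A graded laboratory event therefore does appear in a table.

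What remains undisplayed is a shift that is similar at every volume and is not reported as an adverse event.

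**4. Which pre-dose values exist.** For AST/ALT and CBC, Screening is the only required one; Enrollment repeats are done only if indicated. Creatinine is also required at each dosing visit, but Protocol Table 13 does not say that it is drawn before the gel is given, and the Visit 5 and 7 values follow earlier doses.

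**5. Age of the Screening value.** Screening may be up to 45 days before Enrollment, the first dose is about 14 days after Enrollment, and each washout may last up to 42 days.

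- At 4 mL: 45 + 14 = 59 days.
- At 16 mL: 59 + 42 = 101 days.
- At 32 mL: 101 + 42 = 143 days.

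**6. Precision of a paired summary (illustration only).** The documents give no laboratory SD or correlation ρ. In SD units, the 95% half-width for the mean change is t(0.975; 11) × √(2(1 − ρ)) / √12, with t = 2.201 and 2.201/√12 = 0.635.

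| Assumed ρ | √(2(1 − ρ)) | Half-width (SD) |
|---|---|---|
| 0.3 | 1.183 | 0.75 |
| 0.5 | 1.000 | 0.64 |
| 0.7 | 0.775 | 0.49 |
| 0.9 | 0.447 | 0.28 |

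**The case against.** The strongest reply is that change from baseline is already planned. SAP 5 and Protocol 10.7.2 say it will be analyzed, a general-methods section need not be repeated in every subsection, and post-dose laboratory values are its natural application. This stands to the extent that a reader who inferred that the plan contains no change-from-baseline analysis would be wrong. It does not close the gap: no laboratory variable is named, no baseline is defined, SAP 8.3 does not invoke the method, and SAP 2.3.3 contradicts the tests.

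The second reply is that the adverse event tables will show laboratory problems. A reader might infer that a common shift is invisible in every table; SAP 8.2 does not support that. For hemoglobin, platelets and AST/ALT, any reported Grade 1 or higher event is already a worsening from Screening, so a grade-shift table partly duplicates SAP 8.2. It adds most for WBC (Grade 1 allowed at entry) and creatinine (allowed up to 1.3 times the upper limit of normal).

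Third, a volume-related effect would show between the planned columns, and the undisplayed case needs a similar shift across an eightfold range of volume. That is fair and limits the reach of the point.

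Fourth, baseline means could be worked out by hand from the SAP 7 listings and set beside the post-dose means. That recovers an average difference when data are complete. It gives neither its interval nor the individual changes, because SAP 8.3 specifies no listing of individual post-dose counts or chemistries.

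Finally, change from Screening is an imperfect control. The value may be old, it was selected by entry limits with retesting allowed, and enemas and repeated biopsies intervene. This stands and belongs in a footnote.

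**Conclusion.** The point holds in a limited form. The laboratory tables in SAP 8.3 have no baseline reference, and the general paired method is unassigned and in conflict with SAP 2.3.3. A within-person shift common to all volumes and below adverse event reporting is therefore shown by no table specified in SAP 7 or 8. The planned between-volume contrast has expectation zero for such a shift whatever its size; a paired change would estimate it directly.

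This rests on the text of the two documents and on the crossover of the same participants through all volumes, not on the assumed correlations. The half-widths only indicate what a paired summary of 12 participants could deliver, roughly 0.5 to 0.75 SD at correlations of 0.7 down to 0.3. They should not be read as a measure of power lost by the plan, which proposes no competing baseline test for laboratory data. Nor do the documents show that such a shift is likely at the exposures expected here. The issue is one of reporting and does not touch dosing or clinical management.

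**What to change.** In SAP 8.3:

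- Add a baseline column to the hematology and chemistry tables.
- For each analyte and volume, report the within-participant change at the 24-hour visit, as mean and median with 95% confidence intervals and no p-value. This is consistent with SAP 2.3.3.
- Add a baseline-to-post-dose grade-shift table by volume.
- Define baseline as the last value before the first dose: Screening, or an Enrollment repeat where one was taken. Use Visit 3 creatinine only if it is documented as drawn before dosing.
- State that the hypothesis tests in SAP 5 are not applied to laboratory data, and note that this clarifies the matching sentence in Protocol 10.7.2.
- Footnote that the AST/ALT and CBC baseline may be about 59 days old at the first dose and about 143 days old at the 32 mL dose. Add that selection by entry limits, with retesting allowed, can bias change toward apparent worsening.

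The cost is SAP wording and one or two further tables from data already collected. No visit, sample or procedure is added.

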#### 8.4 Other Safety Measures

Additional safety summaries include:

A listing of participants with abnormal findings on rectal examination after dose insertion (with dose/volume period when finding occurred) will be presented.

Concomitant medications are defined as any medication taken during the study. A participant listing of all concomitant medications will be presented.

# 9. PHARMACOKINETIC ANALYSES

Descriptive statistics will be used to summarize actual PK sample collection times (from dose insertion) for plasma, rectal fluid, rectal tissue, and vaginal fluid samples, and these summaries will be provided by site and overall. Plasma samples are expected to be collected pre-dose and at 1h, 2h, 3h, 4h, 5-6h, and 24h after dose administration. Samples of rectal fluid, rectal tissue, and vaginal fluid (if applicable) are expected to be collected at one of the following time points, 0.5-1h, 1.5-3h, 3.5-5h, or 24h during each dose/volume administration (chosen randomly 1:1:11). These samples are also expected to be collected at 48h after dose administration for one of the three dose/volume levels (4 mL, 16 mL, or 32 mL; chosen randomly 1:1:1).

A table summarizing the number and percentage of plasma, rectal fluid, rectal tissue, and vaginal fluid samples collected outside of the windows of the expected time points will be provided overall and by site. For samples collected outside of the window, a listing of sample collection times along with the amount of time before (-) the window or after (+) the window will be provided. Allowable windows for the collection of plasma, rectal fluid, rectal tissue, and vaginal fluid are detailed in section 5.4.2 and Table 5-1 of the MTN-037 SSP Manual.

#### 9.1 Methods for Handling Missing and BLOQ Data

Each bioanalytical assay for plasma, rectal fluid, rectal tissue, and vaginal fluid has an assay sensitivity described by a lower limit of quantitation (LLOQ). These LLOQs will be reported for each matrix. Concentration values assayed below the LLOQ, as well as those classified as "Not Detected", are identified as below the limit of quantitation (BLOQ).

In individual participant data listings, actual concentration values below the LLOQ will be displayed, if provided from the lab, along with the LLOQ for the assay. For values identified as BLOQ in the data, a listing will be provided displaying the assay and time point(s) of the BLOQ values.

Pre-dose samples that are BLOQ or missing will be assigned a numerical value of zero for the calculation of area under the concentration-time curve (AUC). Pre-dose samples that are missing will be excluded from the concentration summary calculations at pre-dose. Any anomalous quantifiable concentration values (at or above the LLOQ) observed at pre-dose will be identified in the study report and used for the computation of AUC.

Any other BLOQ concentrations that precede quantifiable samples in the initial portion of the profile or a BLOQ value that occurs between quantifiable data points, especially prior to Cmax, will be evaluated to determine if an assigned concentration of zero makes sense, or if reanalysis or exclusion of the data is warranted. Following Cmax, BLOQ values embedded between two quantifiable data points will be treated as missing when calculating AUC. If BLOQ values occur at the end of the collection interval (after the last quantifiable concentration), these will be treated as missing data. If consecutive BLOQ concentrations are followed by quantifiable concentrations in the terminal portion of the concentration curve, these quantified values will be excluded from the PK analysis by assigning them a value of missing, unless otherwise warranted by the concentration-time profile.

Drug concentration-time data will be listed for each participant and summarized by descriptive statistics at each nominal collection time. BLOQ concentrations will be treated as zero for computation of descriptive statistics. Concentrations assigned a value of missing will be omitted from the calculation of descriptive statistics. If the calculated mean concentration is BLOQ, the mean value will be reported as BLOQ, and SD will be reported as ND (not determined). Median, quartiles, minimum and maximum may be reported, and if any of these values are BLOQ, they will be reported as BLOQ.

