#### Rectal Fluid and Rectal Tissue Concentrations

For rectal fluid and rectal tissue, the concentration-time profile will consist of data from different participants at different sampling time points. Individual participant PK parameters will not be calculated for concentration data from rectal fluid and rectal tissue since data were not collected at each time point for each participant.

Displays of rectal fluid and rectal tissue concentration data include:

- For each matrix (RF, RT), tables summarizing the distribution of concentrations at each sampling time point for each dose/volume (3 tables per matrix, or 1 table per matrix with a column for each dose/volume).
- For each matrix (RF, RT), scatter plots of MIV-150 concentration-time data for each dose/volume (3 plots per matrix, or 1 panel per matrix with 3 plots (1 for each dose/volume)).
- For each matrix (RF, RT), plots of mean/median concentration at each time point (with 95% C.I.) for each dose/volume (3 plots per matrix, or 1 panel per matrix with 3 plots (1 for each dose/volume)).
- For each matrix (RF, RT), tables of PK parameters calculated from mean/median concentrations at each sampling time point for each dose/volume (3 tables per matrix).

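### SAP 9.1 carries BLOQ rules suited to individual AUC and ke into the primary concentration summaries, where they can drop measured values and contradict each other; the direction of any bias is undetermined

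*SAP*

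**What the plan says.** SAP 9.1 (Methods for Handling Missing and BLOQ Data) covers plasma, rectal fluid, rectal tissue and vaginal fluid together. Four of its rules matter here.

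- **Late quantifiable values.** "If consecutive BLOQ concentrations are followed by quantifiable concentrations in the terminal portion of the concentration curve, these quantified values will be excluded". They are coded as missing for the PK analysis as a whole, with one override: "unless otherwise warranted by the concentration-time profile".
- **Trailing BLOQ.** "If BLOQ values occur at the end of the collection interval (after the last quantifiable concentration), these will be treated as missing data".
- **Early or embedded BLOQ.** A BLOQ result before the first quantifiable one, or between quantifiable points (chiefly before Cmax), "will be evaluated to determine if an assigned concentration of zero makes sense, or if reanalysis or exclusion of the data is warranted".
- **Summaries.** "BLOQ concentrations will be treated as zero for computation of descriptive statistics", and "Concentrations assigned a value of missing will be omitted from the calculation of descriptive statistics".

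The neighbouring rule for BLOQ values lying between two quantifiable points after Cmax is expressly limited to the AUC calculation. The late-value and trailing-BLOQ rules carry no such limit.

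SAP 9.2 makes the concentrations themselves the primary PK analysis. For rectal fluid and tissue it says that "the concentration-time profile will consist of data from different participants at different sampling time points". SAP 10.2 repeats those analyses for vaginal fluid.

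**The concern.** Setting an isolated late value aside is a recognised convention when fitting one person's terminal slope. It has no such justification in a table of observed concentrations by time point. There, whether a measurement counts would depend on the results around it, and a person with drug present at 24 or 48 h could disappear from the summary.

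The contradiction over trailing BLOQ matters as much. Late time points are where BLOQ results are likely, and the two readings give different means from the same data. The early rule and the late override add discretion with no criterion and no named decision-maker, exercised by people who may know the volume given (SAP 2.3.2: no blinding).

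At stake are the primary concentration summaries at each volume and, for vaginal fluid, a secondary endpoint. The rectal cells hold only three or four results and the vaginal cells one or two, so one changed value can alter what is reported.

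**Working it through.** **1. Sample counts.** SAP 2.3.1 and 2.3.3 give 12 participants, 1:1:1:1 over four time frames and 1:1:1 over the 48 h visits. Per volume that is 12/4 = 3 rectal samples per time frame and 12/3 = 4 at 48 h. This reproduces the figures in SAP 9.2.

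**2. Can the late rule trigger?** It needs two BLOQ results and then a quantifiable one, so at least three results in one profile.

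- *Rectal fluid, rectal tissue, vaginal fluid:* each person gives one sample per volume, plus a 48 h sample at one volume, so at most two. The rule cannot trigger within a person.
- *Plasma:* profiles were simulated with a one-compartment model, using the run-in vaginal gel figures in protocol 2.5 (half-life 4.82 h, Cmax 84.7 pg/mL with CV 48.1%, tmax about 3.9 h). Assumed: CV of ke about 25%, within-person CV 30% or 60%, LLOQ 1 to 20 pg/mL. The rule triggers at 24 or 48 h in at most 0.003% of profiles, and at any time after Cmax in at most 0.12%. With Cmax assumed to be 20, the worst setting gives about 0.01% and about 2%.

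**3. What one late deletion does.** Take 12 results at 24 h, one of them a quantifiable 6 pg/mL that the rule removes:

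| Other 11 results | Mean, kept | Mean, dropped |
|---|---|---|
| all BLOQ = 0 | 6/12 = 0.50 | 0.00 |
| 8 zeros, 3 at 8 | 30/12 = 2.50 | 24/11 = 2.18 |
| 4 zeros, 7 at 12 | 90/12 = 7.50 | 84/11 = 7.64 |

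The mean can move either way. The proportion quantifiable cannot rise: (q−1)/(n−1) ≤ q/n whenever q ≤ n.

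**4. Trailing BLOQ, two readings.** In the same plasma model (Cmax 84.7, within-person CV 30%), the true 24 h mean is about 9.8 pg/mL:

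| LLOQ (assumed) | BLOQ = zero | Trailing BLOQ = missing |
|---|---|---|
| 1 | 9.75 | 10.05 |
| 5 | 8.75 | 13.65 |
| 20 | 3.30 | 31.1 |

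Zero pulls the mean down and missing pushes it up. At LLOQ 20, 89.4% of results are BLOQ.

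**5. The rules combined.** Suppose that at 24 h ten of 12 plasma results are BLOQ and two are 10 pg/mL, each after BLOQ results at 4 h and 5-6 h. The data show 2/12 quantifiable, mean 20/12 = 1.67 and maximum 10. Under the SAP's default both positives go. What remains is 0/10 quantifiable if trailing BLOQ is zero, or no values at all if it is missing and nothing is quantifiable later.

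**6. Early BLOQ.** Excluding k of 12, rather than setting them to zero, multiplies the mean by 12/(12−k): 12/10 = 1.2, 12/8 = 1.5 and 12/6 = 2.0 for k = 2, 4 and 6. Zero is not unbiased either. In the model at 1 h with LLOQ 20, the true mean is 54.2, exclusion gives 56.6 and zero gives 53.3.

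**7. If the late rule were applied to the pooled sparse profile.** With an independent chance p that any sample is quantifiable, a quantifiable result is deleted with probability (1−p)^m, where m is the number of people in the two preceding cells. For rectal matrices m = 3 + 3 = 6, giving 26%, 12% and 2% at p = 0.2, 0.3 and 0.5. For vaginal fluid, with six women placed one or two per time frame and two at 48 h, the average over 24 and 48 h is 46-60% at p = 0.2 and 9-21% at p = 0.5, depending on the split.

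**The case against.** The strongest reply is that the late rule hardly ever acts. Step 2 supports this for plasma, although the model borrows vaginal figures and the protocol says that MIV-150 has never been dosed rectally. The override lets a credible late value stay, and nothing is concealed from the listings: "Drug concentration-time data will be listed for each participant". All of this stands and limits the harm. It does not remove it, because deletion is the default, the override has no criterion, and the summaries rather than the listings are the primary display.

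A reader might infer that the rules bias the results low at late times and high at early times. The documents do not support that. Step 3 shows a late deletion moving the mean either way, trailing BLOQ as missing pushes late means up, and early inflation occurs only if exclusion is chosen over zero.

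A reader might also take the shares in step 7 as expected losses. They need the rule to be applied across people, which the SAP neither states nor excludes, and they assume one constant p from 0.5 to 48 h. Nor do the documents show that early plasma BLOQ is to be expected after rectal dosing, or that BLOQ is commonest at 4 mL.

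**Conclusion.** The point holds as a defect of specification, not as a demonstrated bias in one direction. On the text alone, result-dependent deletions reach the primary concentration summaries, trailing BLOQ has two incompatible treatments there, and early BLOQ can be excluded without criteria.

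The conflict over trailing BLOQ probably has the most practical weight: 8.75 against 13.65 for a true 9.8 pg/mL at LLOQ 5, and 3.30 against 31.1 at LLOQ 20. The late-value rule is probably rare in plasma. In the sparse matrices it is either empty or deletes one person's result because of other people's results, and the SAP should say that it does not apply.

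The model-based sizes are illustrative. Neither an LLOQ nor rectal PK is given, and the within-person variability is assumed.

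**What to change.** In SAP 9.1, separate the rules for concentration summaries from those for AUC and ke:

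1. In concentration tables, figures and composite profiles, for all four matrices, keep every quantifiable post-dose value. Count every post-dose BLOQ value (early, embedded or trailing) as zero, and show the number BLOQ at each time point.
2. Limit the rules that set values to missing (embedded BLOQ, trailing BLOQ, and quantifiable after consecutive BLOQ) to an individual's plasma AUC and ke. State that they do not apply to rectal fluid, rectal tissue or vaginal fluid.
3. In plasma AUC, set post-dose BLOQ values before the first quantifiable value to zero.
4. Exclude or re-assay a result only for a documented assay or collection failure, judged without knowledge of volume.

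The cost is a few sentences and no new data. The downsides are small: an occasional spurious late positive stays in the summaries, where the listings let it be seen, and zero-filling biases means low. That bias is slight when few results are BLOQ and larger when many are, which is why the number BLOQ should be shown.
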